Appendix 2.4 Safety Reporting

Reference Safety Information

The reference for safety information for this study is the maribavir IB, which the sponsor has provided under separate cover to all investigators.

Reporting Procedures

All initial and follow-up SAE reports must be reported by the investigator to the Shire Global Drug Safety Department, the CRO, and Shire Medical Monitor within 24 hours of becoming aware of the event. Note: The 24-hour reporting requirement for SAEs does not apply to reports of abuse, misuse, overdose, or medication errors ([Appendix 2.9](#)) unless they result in an SAE.

The investigator must complete, sign, and date the Shire “Clinical Study Serious Adverse Event for SAEs and Non-serious AEs as Required by Protocol” Form and verify the accuracy of the information recorded on the form with the corresponding source documents (Note: Source documents are not to be sent unless requested), and fax or e-mail the form to the Shire Global Drug Safety Department. A copy of the Shire Clinical Study Serious Adverse Event Form for SAEs and Non-serious AEs as Required by Protocol (and any applicable follow-up reports) must also be sent to the CRO and Shire Medical Monitor using the details specified in the emergency contact information section of the protocol.

Appendix 2.5 Serious Adverse Event Collection Time Frame

All SAEs (regardless of relationship to IP) are collected from the time the subject signs the informed consent until the defined follow-up period stated in Section 7.1.4, and must be reported to the Shire Global Drug Safety Department and the CRO and Shire Medical Monitor within 24 hours of the first awareness of the event.

In addition, any SAE(s) considered “related” to the IP and discovered by the investigator at any interval after the study has completed must be reported to the Shire Global Drug Safety Department within 24 hours of the first becoming aware of the event.

Appendix 2.6 Serious Adverse Event Onset and Resolution Dates

The onset date of the SAE is defined as the date the event meets seriousness criteria. The resolution date is the date the event no longer meets seriousness criteria, the date the symptoms resolve, or the event is considered chronic. In the case of hospitalizations, the hospital admission and discharge dates are considered the onset and resolution dates, respectively.

In addition, any signs or symptoms reported by the subject after signing the informed consent form, or leading up to the onset date of the SAE, or following the resolution date of the SAE, must be recorded as an AE, if appropriate.

Appendix 2.7 Fatal Outcome

Any SAE that results in the subject’s death (eg, the SAE was noted as the primary cause of death) must have fatal checked as an outcome with the date of death recorded as the resolution date. For all other events ongoing at the time of death that did not contribute to the subject’s death, the outcome should be considered not resolved, without a resolution date recorded.

For any SAE that results in the subject's death or any ongoing events at the time of death, unless another IP action was previously taken (eg, drug interrupted, reduced, withdrawn), the action taken with the IP should be recorded as "dose not changed" or "not applicable" (if the subject never received IP or it is a single dose study). The IP action of withdrawn should not be selected solely as a result of the subject's death.

Appendix 2.8 Pregnancy

All pregnancies are to be reported from the time informed consent is signed until the defined follow-up period stated in Section [7.1.4](#).

Any report of pregnancy for any female study participant or the partner of a male study participant must be reported within 24 hours to the Shire Global Drug Safety Department using the Shire Investigational and Marketed Products Pregnancy Report Form. A copy of the Shire Investigational and Marketed Products Pregnancy Report Form (and any applicable follow-up reports) must also be sent to the CRO and Shire Medical Monitor using the details specified in the emergency contact information section of the protocol. The pregnant female study participant must be withdrawn from the study.

In addition to the above, if the investigator determines that the pregnancy meets serious criteria, it must be reported as an SAE using the Shire Clinical Study Serious Adverse Event and Non-serious AEs Required by the Protocol Form as well as the Shire Investigational and Marketed Products Pregnancy Report Form. The test date of the first positive serum/urine β -HCG test or ultrasound result will determine the pregnancy onset date.

Pregnancy complications such as spontaneous abortion/miscarriage, elective abortion or congenital abnormality are considered SAEs and must be reported using the Shire Clinical Study Serious Adverse Event and Non-serious AEs Required by the Protocol Form.

Every effort should be made to gather information regarding the pregnancy outcome and condition of the infant. It is the responsibility of the investigator to obtain this information within 30 calendar days after the initial notification and approximately 30 calendar days and 1 year post-partum.

Appendix 2.9 Abuse, Misuse, Overdose, and Medication Error

Abuse, misuse, overdose, or medication error (as defined below) must be reported to the sponsor according to the SAE reporting procedure whether or not they result in an AE/SAE as described in [Appendix 2.4](#).

Note: The 24-hour reporting requirement for SAEs does not apply to reports of abuse, misuse, overdose, or medication errors unless these result in an SAE.

The categories below are not mutually exclusive; the event can meet more than 1 category.

- **Abuse** – Persistent or sporadic intentional intake of IP when used for a non-medical purpose (eg, to alter one’s state of consciousness or get high) in a manner that may be detrimental to the individual and/or society
- **Misuse** – Intentional use of IP other than as directed or indicated at any dose (Note: this includes a situation where the IP is not used as directed at the dose prescribed by the protocol)
- **Overdose** – Intentional or unintentional intake of a dose of IP higher than the protocol-prescribed dose
- **Medication Error** – An error made in prescribing, dispensing, administration, and/or use of an IP. Medication errors should be collected/reported for all products under investigation. The administration and/or use of the unassigned treatment, or the administration and/or use of an expired IP is/are always reportable as a medication error.

Cases of subjects missing doses of the IP should be reported as missed dose.

Appendix 2.10 Urgent Safety Measures

An urgent safety measure is an immediate action taken, which is not defined by the protocol, in order to protect subjects participating in a clinical trial from immediate harm, these do not constitute de facto deviation from the protocol. Urgent safety measures may be taken by the sponsor or clinical investigator, and may include any of the following:

- Immediate change in study design or study procedures
- Temporary or permanent halt of a given clinical trial or trials
- Any other immediate action taken in order to protect clinical trial participants from immediate hazard to their health and safety

The investigator may implement urgent safety measures to protect study subjects from immediate hazard to their health or safety. The measures should implement immediately and does not require prior authorization from the sponsor. In the event(s) of an apparent direct hazard to the subject, the investigator will notify the sponsor immediately by phone and confirm notification to the sponsor in writing as soon as possible, and within 1 calendar day after the change is implemented. The sponsor will also ensure the responsible IRB(s)/EC(s) and relevant competent authority(s) are notified of the urgent safety measures taken in such cases according to local regulations.

Appendix 2.11 Regulatory Agency, Institutional Review Board, Ethics Committee, and Site Reporting

The sponsor is responsible for notifying the relevant regulatory authorities, IRBs and ECs of related, unexpected SAEs.

In addition, the sponsor is responsible for notifying active sites of all related, unexpected SAEs occurring during all interventional studies across the TAK-620 program.

The investigator is responsible for notifying the local IRB/EC of SAEs or significant safety findings, or the relevant local regulatory authority of all SAEs that occur at his or her site as required by IRB/EC procedures.

**REVISION HISTORY**

Version	Issue Date	Summary of Changes
1.0	06 Aug 2020	Final Version

## ABBREVIATIONS

AE	adverse event
AUC	area under the curve
AUC 0-inf	area under the curve extrapolated to infinity, calculated using the observed value of the last non-zero concentration
AUC 0-inf %extrap	the percent of AUC 0-inf extrapolated, calculated by $(1 - AUC_{last}/AUC_{0-inf}) * 100$
AUC last	area under the curve from the time of dosing to the last measurable concentration
β-HCG	beta-human chorionic gonadotropin
BLQ	below limit of quantification
BMI	body mass index
CI	confidence interval
C max	maximum concentration
CL/F	oral clearance
CRF	case report form
CV	coefficient of variation
CV%	percent coefficient of variation
ECG	electrocardiogram
IP	investigational product, maribavir
λ z	first order rate constant associated with the terminal (log linear) portion of the curve
PK	pharmacokinetics
PT	preferred term
QTc	corrected QT interval
QTcF	corrected QT interval by Fridericia's formula
SAE	serious adverse event
SAP	statistical analysis plan
SOC	system organ class
t 1/2	terminal half-life
TEAE	treatment-emergent adverse event

TOST	two one-sided test
$T_{lag}$	delay between the time of dosing and time of appearance of drug concentration in plasma in the employed sampling scheme
$t_{max}$	time of maximum observed concentration sampled during a dosing interval
TSH	thyroid-stimulating hormone
$V_z/F$	apparent volume of distribution

## 1. INTRODUCTION

This statistical analysis plan (SAP) provides a technical and detailed elaboration of the statistical analyses of pharmacokinetic (PK), safety, and tolerability data as described in the TAK-620-1020 protocol amendment 1 dated 08 July 2020. Specifications for tables, figures, and listings will be contained in a separate document. Methods used in the final analysis of pharmacokinetic (PK) parameters and the reporting of the results from these analyses will be described in Clinical Pharmacology Analysis Plan (CPAP).

Within this document, the term investigational product is used to refer to maribavir.

## 2. OBJECTIVES AND ENDPOINTS

### 2.1 Objectives

#### 2.1.1 Primary Objective

- To compare the PK profile of maribavir, administered as a single oral dose at 400 mg, between healthy, adult subjects of Japanese descent and matched, healthy, adult, non-Hispanic, Caucasian subjects.

#### 2.1.2 Secondary Objectives

- To assess the dose proportionality of maribavir PK following single oral doses of 200 mg, 400 mg, and 800 mg of maribavir in healthy, adult subjects of Japanese descent.
- To assess the safety and tolerability of single oral doses of 200 mg, 400 mg, and 800 mg of maribavir in healthy, adult subjects of Japanese descent.
- To evaluate the safety and tolerability of a single 400 mg oral dose of maribavir in matched, healthy, adult, non-Hispanic, Caucasian subjects.

#### 2.1.3 Exploratory Objective

- 

### 2.2 Endpoints

#### 2.2.1 Pharmacokinetic Endpoints

##### Primary Pharmacokinetic Endpoints

Maribavir  $C_{max}$ ,  $AUC_{last}$ , and  $AUC_{0-inf}$  will be the primary endpoints.

PK parameters will include, but not be limited to the following:

- $C_{max}$  Maximum observed plasma concentration
- $t_{max}$  Time of maximum observed concentration sampled during a dosing interval
- $AUC_{last}$  Area under the curve from the time of dosing to the last measurable concentration
- $AUC_{0-inf}$  Area under the curve extrapolated to infinity, calculated using the observed value of the last non-zero concentration
- $AUC_{0-inf}\%extrap$  The percent of  $AUC_{0-inf}$  extrapolated, calculated by  $(1 - AUC_{last}/AUC_{0-inf}) * 100$
- $\lambda_z$  elimination rate in the terminal phase
- $t_{1/2}$  Terminal half-life

- CL/F Apparent total body clearance following extravascular administration calculated as dose divided by  $AUC_{0-inf}$
- $V_z/F$  Apparent volume of distribution following extravascular administration calculated as CL/F divided by  $\lambda_z$
- $T_{lag}$  Delay between the time of dosing and time of appearance of plasma concentration in the employed sampling scheme

In addition, dose-normalized (to 400 mg)  $C_{max}$ ,  $AUC_{last}$ , and  $AUC_{0-inf}$  will be calculated for Japanese subjects.

### 2.2.2 Exploratory Pharmacokinetic Endpoints

### 2.2.3 Safety Endpoints

The safety analysis will be performed using the Safety Analysis Set. Safety endpoints include AEs, vital signs, ECG variables, and clinical laboratory variables. The following safety evaluations will be performed:

- Number, severity, seriousness, and causality of treatment-emergent adverse events (TEAEs).
- Changes in vital signs, ECGs, and clinical laboratory results (hematology, chemistry, and urinalysis) from baseline to post-baseline time points.

For each safety variable, the last value collected before the first dose of investigational product in that period will be used as baseline for all analyses of that safety variable in that period.

### 3. STUDY DESIGN

#### 3.1 General Description

This is a Phase 1, open-label, randomized, crossover, partially fixed sequence, single-center study. A total of 24 subjects will be enrolled: 12 subjects of Japanese descent and 12 non-Hispanic, Caucasian subjects. Non-Hispanic, Caucasian subjects will be matched to Japanese subjects based on age ( $\pm 10$  years), sex, and body mass index (BMI) ( $\pm 15\%$ ).

[figure not shown]
#### **Treatment Period:**

The non-Hispanic, Caucasian subjects will have one Treatment Period. The Japanese subjects will have Treatment Periods 1, 2, and 3.

- In Treatment Period 1, all study subjects (both Japanese and Caucasian) will receive maribavir as a single 400 mg oral dose.
- Depending upon the randomization assignment on Day 1 of treatment period 2, all subjects of Japanese descent will be dosed in a crossover fashion in Treatment Periods 2 and 3. They will receive a single oral dose of either 200 mg followed by 800 mg maribavir or a single oral dose of 800 mg followed by 200 mg maribavir.

The study design flow chart is presented in [Figure 1](#).

Figure 1 Study Design Flow Chart

\*Washout period of 72 to 73 hours after treatment on Day 1.

### **3.2 Randomization**

Subjects of Japanese descent who meet all the inclusion criteria and none of the exclusion criteria will be randomized (1:1 ratio) to either maribavir 200 mg or 800 mg on Day 1 in treatment period 2. Subjects will then be dosed in a crossover fashion with a single dose of maribavir based on their randomization assignment on Day 1 in Treatment Periods 2, and 3. There is no stratification for this study.

### **3.3 Blinding**

This is an open-label study. Blinding is not applicable.

### **3.4 Sample Size and Power Considerations**

The sample size consideration for the primary objective of evaluating the PK profile of maribavir, administered as a single oral dose at 400 mg, between Japanese subjects and matched, healthy, adult, non-Hispanic, Caucasian subjects is based on study feasibility and comparable studies.

A total of 24 subjects (12 subjects of Japanese descent and 12 matched, non-Hispanic, Caucasian subjects) will be targeted to be enrolled in the study.

## **4. STATISTICAL ANALYSIS SETS**

### **4.1 Enrolled Set**

The Enrolled Set consists of all subjects who have signed informed consent and also met inclusion/exclusion criteria.

### **4.2 Safety Set**

The Safety Set consists of subjects who are administered at least 1 dose of investigational product (maribavir) and have at least 1 post-dose safety assessment. Analysis will be performed according to the treatment regimen actually received regardless of the randomized treatment regimen.

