7.1.1.1 Screening Failure

A screen failure is a subject who has given informed consent and failed to meet the inclusion and/or met at least 1 of the exclusion criteria and has not been randomized or administered IP.

For purposes of data collection, all subjects who give consent to the study, but are not enrolled and/or randomized will be reported as screen failures even if they were otherwise fully eligible for the study, for example alternates/reserve subjects.

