8.6 Study Population

The **Enrolled Set** will consist of all subjects who have signed informed consent and also passed inclusion/exclusion criteria.

The **Safety Set** will consist of all subjects who receive any amount of IP. Analysis will be performed according to the treatment regimen actually received regardless of the randomized treatment regimen.

The **Pharmacokinetic (PK) Set** will consist of subjects who receive at least 1 dose of study drug and have evaluable post-dose maribavir PK data (defined as complete concentration-time profile to obtain meaningful estimates of PK parameters). The PK analyses will be based on this analysis population.

Subjects who do not provide reliable concentration-time profile (in 1 or more periods) may be excluded from PK analysis (for the corresponding treatment period).

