## 5. STUDY SUBJECTS

### 5.1 Disposition of Subjects

The number of subjects who were included in each defined statistical analysis set (Enrolled, Safety, and PK) will be summarized by cohort and overall.

Summaries and listing of subject disposition will be based on the Enrolled Set.

The reasons for exclusion from the PK set will be presented in the listings with details of any AEs.

The number and percentage of subjects who completed and prematurely discontinued the study, as well as subjects who completed dosing and prematurely discontinued the study drug, as recorded on the termination page of the electronic case report form (eCRF), will be presented for each cohort and overall for the Safety Set. Reasons for premature discontinuation from the study, as well as discontinuation from study drug, as recorded on the termination page of the eCRF will be summarized (number and percentage) by cohort and overall, for the Safety Set. All subjects who prematurely discontinued the study and/or discontinued the study drug will be listed by discontinuation reason.

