## 7. SAFETY ANALYSIS

The safety analysis will be performed using the Safety Set. Safety variables include AEs, vital signs, ECG, and clinical laboratory variables. For each safety variable, the last value collected before the first dose of investigational product will be used as baseline for all analyses of that safety variable. Last Value on Treatment (LVOT) will be defined as the last valid assessment obtained after Baseline and until 7 days after last dose of investigational product.

All safety analyses will be conducted according to the treatment the subject actually received.

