#### **14. CHANGES TO ANALYSIS SPECIFIED IN PROTOCOL**

The following change is made to this statistical analysis:

- More clarification is added for the Safety Analysis Set.

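### SAP 4.2 narrows the protocol's Safety Set under the label of a clarification, and SAP 5.1 names two different sets for disposition

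*SAP*

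**What the plan says.** Protocol 8.6 (repeated in the synopsis) says that the Safety Set "will consist of all subjects who receive any amount of IP". It sets no condition on what is observed afterwards.

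SAP 4.2 limits the set to subjects who are "administered at least 1 dose of investigational product (maribavir) and have at least 1 post-dose safety assessment". The SAP does not say what counts as a post-dose safety assessment. SAP 14, the section for departures from the protocol, has one entry: "More clarification is added for the Safety Analysis Set".

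The set is used widely. SAP 7 states: "The safety analysis will be performed using the Safety Set". Exposure (SAP 5.6), compliance (SAP 5.7) and protocol deviations (SAP 5.8) are also summarised on it.

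On disposition, SAP 5.1 first says: "Summaries and listing of subject disposition will be based on the Enrolled Set". In the same section, the numbers completing and discontinuing study and drug "will be presented for each cohort and overall for the Safety Set", and the reasons for discontinuation are put on the Safety Set too. The section also promises a count of subjects in each analysis set by cohort, and a listing of all subjects who discontinued, by reason, with no Safety Set limit attached.

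**The concern.** A safety population that requires data after dosing is conditioned on follow-up. The subject it can lose is one who was dosed and then left before anything was recorded, and early losses of that kind are what safety and discontinuation tables should show. The protocol's definition cannot lose that subject; the SAP's can.

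Two drafting faults make this worse. A reader who relies on SAP 14 to learn what changed would not discover that a dosed subject can now be left out. And a programmer cannot follow both statements in SAP 5.1 when building the completion and discontinuation table, so the choice of denominator is left open until the data are in hand. With 12 subjects per cohort, one subject is a visible share of a column.

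**Working it through.** The plan gives no figure to reproduce here: the sample size of 24 (12 + 12) rests on feasibility and comparable studies. The check is a comparison of definitions, followed by simple proportions.

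**1. Definitions side by side**

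- Protocol 8.6: one condition, receipt of any investigational product.
- SAP 4.2: two conditions, at least one dose and at least one post-dose safety assessment.

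The SAP set is therefore contained in the protocol set. On the assessment condition, the two differ by the dosed subjects with no post-dose safety assessment.

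**2. When the difference can arise**

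- The condition applies once per subject, not once per period. A Japanese subject with any safety assessment after the Period 1 dose stays in the set whatever happens in Periods 2 and 3. The rule therefore bites only after the first dose.
- After that dose, adverse events, vital signs and ECG are scheduled at 3 and 24 hours (Protocol Tables 2 and 6), and subjects stay in the unit until at least Day 2.
- Protocol 4.5 asks for early-withdrawal evaluations as completely as possible, and Protocol 7.1.4 adds a follow-up call. These are to be attempted; they are not guaranteed.

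A subject would have to leave before the 3-hour checks, miss the withdrawal evaluations and not be reached afterwards. That is possible but rare.

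**3. Size if one such subject occurs** (illustrative assumption: exactly one, and the only discontinuation)

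| | Protocol set | SAP set |
|---|---|---|
| Cohort, not replaced | 1/12 = 8.3% | 0/11 = 0% |
| Both cohorts, not replaced | 1/24 = 4.2% | 0/23 = 0% |
| Cohort, replaced | 1/13 = 7.7% | 0/12 = 0% |
| Both cohorts, replaced | 1/25 = 4.0% | 0/24 = 0% |

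Protocol 4.5 allows replacement, at the sponsor's discretion, of a subject who does not complete the Period 1 PK assessments. With replacement, the Safety Set table would show a full column of 12 with no discontinuation.

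**4. Adverse events**

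Incidence changes only if the lost subject had an event and that event is not itself treated as a safety assessment, a question the SAP leaves open. If it is not, and two of 12 subjects had the event including the lost one, 2/12 = 16.7% becomes 1/11 = 9.1%.

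**5. What does not change**

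The percentages of potentially clinically significant laboratory, vital-sign and ECG values already require a post-baseline assessment in the denominator (SAP 7.2 to 7.4). The primary PK comparison uses the PK Set (SAP 4.3).

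**6. SAP 5.1**

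Completion, discontinuation and reasons are what a disposition summary normally contains. The first statement puts them on the Enrolled Set and the later sentences put them on the Safety Set. For the subject in step 3, the two readings give different tables.

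**The case against.** The strongest reply is that the condition is almost inert. The study is resident, dosing is observed, several assessments follow within a day, and a follow-up call is planned with at least three documented contact attempts. Adverse events are themselves safety variables in SAP 7, so a reported event could reasonably satisfy the condition; on that reading no recorded event is lost. There is also a statistical argument for the restriction: a subject never observed counts as event-free if kept. With three subjects affected, keeping such a subject alongside a replacement gives 3/13 = 23.1% instead of 3/12 = 25.0%. All of this stands as to size. It does not explain why a restriction is called a clarification, and it leaves SAP 5.1 inconsistent.

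Three stronger readings are tempting, and the documents do not support them.

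- A reader might infer that the subject vanishes from disposition altogether. An eligible subject remains in the Enrolled Set, any gap shows in the table of analysis-set counts, and the listing of discontinued subjects carries no Safety Set limit.
- A reader might infer that SAP 4.2 demands a complete dose and so excludes partial intake. The text asks for at least one dose and never says full or complete. The wording is looser than the protocol's and is better aligned, but the exclusion is not stated.
- A reader might infer that the Enrolled Set is also faulty because it admits undosed reserves. SAP 4.1, which "consists of all subjects who have signed informed consent and also met inclusion/exclusion criteria", matches Protocol 8.6 in substance. Protocol 7.1.1.1 says that consenting subjects who are not enrolled or randomised, reserves among them, "will be reported as screen failures even if they were otherwise fully eligible for the study"; it does not treat them as enrolled. No number of reserves is given.

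**Conclusion.** The point holds and is minor. SAP 4.2 is narrower than Protocol 8.6, SAP 14 does not disclose that, and SAP 5.1 gives two sets for the same table. All three follow from the text whether or not an affected subject ever appears.

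The numerical effect depends on a dosed subject having no post-dose safety assessment of any kind; withdrawing soon after dosing is not enough. If one such subject occurs, that subject is missing from the safety, exposure and compliance denominators, and the Safety Set discontinuation rate in the cohort moves from 8.3% to zero, or from 7.7% to zero with replacement. The loss would be traceable for an eligible subject, but not from the tables a reader would consult first. If every dosed subject has at least one assessment, no result changes.

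**What to change.** 1. In SAP 4.2, restore the protocol's definition: all subjects who receive any amount of investigational product, analysed by treatment actually received.
2. Correct SAP 14 to match. With the protocol definition restored, there is no Safety Set change left to report.
3. In SAP 5.1, name one set for completion, discontinuation and reasons, and make sure it includes every dosed subject. The restored Safety Set does this. The Enrolled Set can still carry the analysis-set counts.

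The Enrolled Set definition can stay as it is. The cost is a few lines of SAP text. No protocol amendment is needed, because the change returns the SAP to the protocol. Should an affected subject occur, the safety tables would carry that subject in the denominator with no post-dose values, and a footnote would be enough to say so.
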